The analysis for QTcF for CBP-307 versus placebo will be based on a linear mixed-effects model with change-from-baseline QTcF ($\Delta QTcF$) as the dependent variable, time (ie, postbaseline timepoints on Days 1, 6, and 15: categorical), treatment (therapeutic dose of CBP-307 and supratherapeutic dose of CBP-307 on Day 15, and corresponding placebo), and time-by-treatment interaction as fixed effects. An unstructured covariance matrix will be specified for the repeated measures at postdose timepoints within subjects. If the model with unstructured covariance matrix fails to converge, other covariance matrices such as compound symmetry and autoregressive will be considered. From this analysis, the LS mean, SE, and 2-sided 90% CIs will be calculated for the contrast “CBP-307 versus placebo” for each day of Days 1, 6, and 15 at each postbaseline timepoint on Days 1, 6, and Day 15, respectively.

The by-time point analysis for QTcF will be also performed for moxifloxacin versus placebo at postbaseline timepoints on Day 1 and Day 16. A linear mixed-effects model will be used with $\Delta QTcF$ as the dependent variable and time (ie, postbaseline timepoints on Days 1 and 16:

categorical), treatment (moxifloxacin and placebo), sequence (placebo/moxifloxacin or moxifloxacin/placebo), and time-by-treatment interaction as fixed effects. An unstructured covariance matrix will be specified for the repeated measures at postbaseline timepoints for subject within visit. The model will also include a subject-specific random effect. If the model with an unstructured covariance matrix fails to converge, other covariance matrices, such as compound symmetry or autoregressive, will be considered. From this analysis, the LS mean, SE, and 2-sided 90% CIs will be calculated for the contrast “moxifloxacin versus placebo” at each postbaseline timepoint, respectively.

For HR, PR, and QRS intervals, the analysis will be based on the change-from-baseline postdose (Δ HR, Δ PR, Δ QRS). The same (by-timepoint analysis) model will be used as described for QTcF. The LS mean, SE, and 90% CI from the statistical modeling for both change-from-baseline and placebo-corrected change-from-baseline values will be listed in the tables and graphically displayed.

Categorical Analyses

The analysis results for categorical outliers, T-wave morphology, and U-wave presence will be summarized in frequency tables with counts (percentages) for both the number of subjects and the number of timepoints. For categorical outliers, the number (percentage) of subjects as well as timepoints who had increases in absolute QTcF values >450 and ≤ 480 msec, >480 and ≤ 500 msec, or >500 msec, and changes from predose baseline of >30 and ≤ 60 msec, or >60 msec; increase in PR from predose baseline $>25\%$ to a PR > 200 msec; increase in QRS from predose baseline $>25\%$ to a QRS >120 msec; decrease in HR from predose baseline $>25\%$ to an HR <50 bpm; and increase in HR from predose baseline $>25\%$ to an HR >100 bpm will be determined. For T-wave morphology and U-wave presence, the analyses will be focused on change from baseline (ie, treatment-emergent changes).

Section 8.4, Pharmacokinetic Analyses, paragraph 2

Previously read:

For each subject, the following PK parameters will be calculated, whenever possible, based on the plasma concentration for CBP-307 and moxifloxacin, according to the model independent approach:

- C_{\max}
- t_{\max}
- AUC_{0-24}
- AUC_{∞}
- apparent terminal elimination rate constant (λ_Z)
- $t_{1/2}$

- apparent total clearance (CL/F)
- apparent volume of distribution during the terminal phase (V_z/F)

Now reads:

For each subject, the following PK parameters will be calculated, whenever possible, based on the plasma concentration for CBP-307 and moxifloxacin, according to the model independent approach:

- C_{max}
- t_{max}
- AUC₀₋₂₄
- AUC_{inf}
- apparent terminal elimination rate constant (λ_Z)
- t_{1/2}
- apparent total clearance (CL/F)
- apparent volume of distribution during the terminal phase (V_z/F)
- Accumulation ratio (R_{ac}) for C_{max} (R_{ac[Cmax]}) and R_{ac(AUC0-24)}, calculated as Day 15 C_{max}/Day 7 C_{max} and Day 15 AUC₀₋₂₄/Day 7 AUC₀₋₂₄, respectively.

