Appendix 2: Clinical Laboratory Evaluations

Clinical chemistry:	Hematology:	Urinalysis:
Alanine aminotransferase Albumin Alkaline phosphatase Aspartate aminotransferase Calcium Chloride Cholesterol Creatinine Direct bilirubin ^a Gamma-glutamyl transferase Glucose Indirect bilirubin ^a Inorganic phosphate Magnesium Potassium Sodium Total bilirubin Total protein Urea Uric acid	Hematocrit Hemoglobin Mean cell hemoglobin Mean cell hemoglobin concentration Mean cell volume Platelet count Red blood cell count White blood cell (WBC) count WBC differential: Basophils Eosinophils Lymphocytes Monocytes Neutrophils	Blood Glucose Ketones Leukocyte esterase Nitrite pH Protein Specific gravity Urobilinogen Microscopic examination (if indicated by dipstick)
Serology:	Drug screen:	Hormone panel - females only:
Anti-hepatitis B surface antibody Anti-hepatitis B core antibody Hepatitis B surface antigen Hepatitis C antibody Human immunodeficiency (HIV-1 and HIV-2) antibodies and p24 antigen Syphilis	Including but not limited to: Amphetamines/methamphetamines Barbiturates Benzodiazepines Cocaine (metabolite) Methadone Phencyclidine Opiates Tetrahydrocannabinol Tricyclic antidepressants Cotinine test	Follicle-stimulating hormone (postmenopausal females only) Serum pregnancy test (human chorionic gonadotropin) ^b Urine pregnancy test Other Tests Low density lipoprotein cholesterol High-density lipoprotein cholesterol Triglycerides

^a Direct and indirect bilirubin will be analyzed if total bilirubin is elevated.

^b Serum pregnancy test will be performed at screening and urine pregnancy tests will be performed on Day -2 and at the follow-up visit (on Day 29±2 days). A positive urine pregnancy test will be confirmed with a serum pregnancy test.

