Appendix 6: Schedule of Assessments

Schedule of Assessments															
Study Period	Screening	In-house Treatment Period													End-of-Study/Follow-up Visit
Study Day(s)	-28 to -3	-2	-1	1	2	3 to 5	6	7 to 14	15	16	17	18	19	29±2	
Informed consent	X														
Eligibility criteria review (Inclusion/Exclusion)	X	X													
Demographics	X														
Medical history	X														
Admission to clinical research unit ¹		X													
Discharge from clinical research unit ²													X		
Randomization				X											
Vital signs ^{3,8}	X	X	X	X	X	X	X	X	X	X	X	X	X		
Height/weight/BMI	X														
Physical exam	X	X												X	
Hematology	X	X					X						X	X	
Clinical chemistry (including cholesterol panel tests)	X	X					X						X	X	
Urinalysis	X	X											X	X	
Serology for HIV-1/HIV-2 antibodies and p24 antigen, HBsAb, HBcAb, HBsAg, or HCVAb		X													
12-lead safety electrocardiogram ^{4,8}	X	X	X	X	X	X	X	X	X	X			X	X	
Cardiac Telemetry Monitoring ⁹				X	X	X (Day 3)		X (Day 7)							

Schedule of Assessments														
Study Period	Screening	In-house Treatment Period												End-of-Study/Follow-up Visit
Study Day(s)	-28 to -3	-2	-1	1	2	3 to 5	6	7 to 14	15	16	17	18	19	29±2
Breath alcohol, urine drug toxicology and cotinine	X	X												
Cardiodynamic monitoring (Holter)/replicate ECG extraction ⁵			X	X			X		X	X				
Pregnancy test ⁶	X	X												X
Follicle -stimulating hormone test (postmenopausal females only)	X													
CBP-307/placebo administration			X	X	X	X	X	X	X	X				
Moxifloxacin/placebo administration				X						X				
Blood sampling for PK ^{7,8}				X			X		X	X		X	X	
Adverse event monitoring	X	X	X	X	X	X	X	X	X	X	X	X	X	X
Concomitant medication recording	X	X	X	X	X	X	X	X	X	X	X	X	X	X

Abbreviations: BMI = body mass index; ECG = electrocardiogram; HBsAg = hepatitis B surface antigen; HCVAb = hepatitis C virus antibodies; HIV = human immunodeficiency virus; PK = pharmacokinetic.

1. Subjects will be asked to arrive at the clinical site in the afternoon 2 days before start of dosing on Day 1 (Day -2).
2. Discharge from unit will occur after the 96-hour PK samples and after completion of safety assessments on Day 19.

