3. INVESTIGATIONAL PLAN

3.1. Overall Study Design and Plan

This will be a Phase I, randomized, double-blind, double-dummy, placebo-controlled, positive-controlled, single-site, 3-arm study to investigate the effects of therapeutic and supratherapeutic oral doses of CBP-307 on the QTc interval in healthy male and female subjects.

Potential subjects will be asked to read and sign an informed consent form (ICF). After informed consent is obtained, screening procedures and tests to establish subject eligibility to enter the study will be performed within 28 days before Day 1. After informed consent has been obtained but prior to the initiation of study treatment administration, only SAEs will be reported. After placebo administration to all subjects on Day -1, all AEs, whether

volunteered, elicited, or noted upon physical examination, will be recorded throughout the study (ie, from Day -1 until the end of the study).

In this study, approximately 64 healthy subjects (at least 30% for each sex) will be randomized into 2 groups (Group 1 and 2) with 32 subjects in each. Group 2 consists of 2 sub-groups (Group 2A and 2B) and each sub-group will be randomized with 16 subjects. Randomized subjects will receive the assigned study drug as a single dose in the morning on Days 1, 2, 3 to 6, 7 to 15, and on Day 16 (placebo will be administered to all subjects on Day -1).

[figure not shown]
The following treatments will be administered:

- Starting doses of CBP-307 for titration (0.05 mg on Day 1 followed by an up-titrated dose of 0.1 mg on Day 2)
- A therapeutic dose of CBP-307 (0.2 mg, Days 3 to 6)
- A supratherapeutic dose of CBP-307 (0.5 mg, Days 7 to 15)
- Placebo (matched to moxifloxacin and CBP-307)
- Moxifloxacin (400 mg)

Moxifloxacin will be used as a positive control to determine the assay sensitivity of this study with an expected peak QT effect (placebo-corrected change-from-baseline QTcF; $\Delta\Delta\text{QTcF}$) of 10 to 15 msec.

An overview of the study design is shown in [Figure 1](#).

Figure 1: Study Schematic

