4.2. Exclusion Criteria

Subjects will be excluded from the study if they satisfy any of the following criteria at the screening visit unless otherwise stated:

1. Subject is mentally or legally incapacitated or has had significant history of recent mental health issues requiring medication and/or hospitalization at the time of the screening visit or expected during the conduct of the study.

2. Significant history or clinical manifestation of any metabolic, allergic, dermatological, hepatic, renal, hematological, pulmonary, cardiovascular, gastrointestinal, neurological, respiratory, endocrine, or psychiatric disorder, as determined by the investigator (or designee). *Note: Childhood asthma that is considered recovered or seasonal allergies that are not currently active or requiring treatment are allowed.*
3. History of significant hypersensitivity, intolerance, or allergy to any drug compound, food, or other substance, unless approved by the investigator (or designee).
4. History or presence of hypersensitivity or idiosyncratic reaction to the study drugs, related compounds, or inactive ingredients.
5. History of significant multiple and/or severe allergies (eg, latex allergy, band-aids, adhesive dressing, or medical tape), or has had an anaphylactic reaction or significant intolerance to prescription or nonprescription drugs.
6. History of stomach or intestinal surgery or resection that would potentially alter absorption and/or excretion of orally administered drugs within 6 months prior to the first dose of study drug (uncomplicated appendectomy and hernia repair will be allowed).
7. History or presence of:
 - a. Hypokalemia, in the opinion of the investigator (or designee);
 - b. Risk factors for Torsades de Pointes (eg, heart failure, cardiomyopathy, or family history of Long QT Syndrome);
 - c. Sick sinus syndrome, second, or third degree atrioventricular block, myocardial infarction, pulmonary congestion, cardiac arrhythmia, prolonged QT interval, or conduction abnormalities;
 - d. Repeated or frequent syncope or vasovagal episodes;
 - e. Hypertension, angina, bradycardia, or severe peripheral arterial circulatory disorders.
8. Clinically significant abnormalities (as judged by the investigator in laboratory tests results [out-of-range results confirmed on repeat]), including but not limited to the following parameters:

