 - a. alanine aminotransferase, aspartate aminotransferase, alkaline phosphatase, or total bilirubin greater than $1.5 \times$ upper limit of normal;
 - b. hemoglobin <10 g/dL, WBC $<3.0 \times 10^9$ /L, neutrophils $<1.5 \times 10^9$ /L, lymphocytes $<0.8 \times 10^9$ /L and platelets $<100 \times 10^9$ /L or $>1200 \times 10^9$ /L;
9. History or evidence of alcoholism or drug/chemical abuse within 2 years prior to check-in.
10. Alcohol consumption of >10 units per week for males and females. One unit of alcohol equals $\frac{1}{2}$ pint (285 mL) of beer or lager, 1 glass (125 mL) of wine, or $\frac{1}{6}$ gill (25 mL) of spirits.
11. Positive alcohol breath test result or positive urine drug screen (confirmed by repeat) at screening or check-in.

12. Positive hepatitis panel, positive syphilis test, and/or positive human immunodeficiency virus test ([Appendix 2](#)).
13. Participation in a clinical study involving administration of an investigational drug (new chemical entity) in the past 28 days prior to the first dose of study treatment on Day 1. The 28-day window will be derived from the date of the last blood collection or dosing, whichever is later, in the previous study to Day 1 of the current study.
14. Participation in a previous clinical study where subjects received CBP-307.
15. Administration of a Coronavirus Disease 2019 (COVID-19) vaccine in the past 28 days prior to first dose of study treatment on Day 1.
16. Use or intend to use any prescription medications/products within 14 days prior to first dose of study drug (Day 1) and throughout the study, unless deemed acceptable by the investigator (or designee). *Note: For females only, the use hormonal contraception, hormone replacement therapy or oral, implantable, transdermal, injectable, or intrauterine hormonal contraceptives within 14 days prior to Day 1 is not acceptable, except for Mirena®.*
17. Use or intend to use any drugs known to be significant inhibitors or inducers of CYP enzymes and/or P-gp, including St. John's Wort, for days prior to the first dose of study drug and throughout the study. Appropriate sources will be consulted by the investigator or designee to confirm the lack of PK/PD interaction with the study drug.
18. Use or intend to use slow-release medications/products considered to still be active within 14 days prior to check-in, unless deemed acceptable by the investigator (or designee).

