7. STUDY ASSESSMENTS AND PROCEDURES

Every effort will be made to schedule and perform the procedures as closely as possible to the nominal time, giving considerations to appropriate posture conditions, practical restrictions, and the other procedures to be performed at the same timepoint.

The highest priority procedures will be performed closest to the nominal time. The order of priority for scheduling procedures around a timepoint is (in descending order of priority):

- dosing
- continuous ECG extraction window
- pharmacokinetic blood samples
- safety assessments
- any other procedures.

This study includes a screening period (Day -28 to Day -3), a treatment period (Days -2 to 19), and a follow-up period (Day 29 ±2 days).

The defined abnormal vital sign measurements (Exclusion Criteria #4) at check-in (Day -2) or baseline (Day -1 predose) will only be considered exclusionary if judged applicable by the investigator. For confirmation of enrollment eligibility based on pulse rate, the pulse rate assessed by vital signs, rather than the 12-lead ECG, will be used. For all subjects, the screening, check-in, or baseline blood pressure, pulse rate, and respiratory rate may be repeated after 5 to 10 minutes if the initial reading is believed to be atypical for the subject.

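### Exclusion 12 applies at the screening visit, but the schedule marks viral serology only on Day -2, gives the syphilis test no row, and no text requires the results before baseline procedures or dosing

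*Protocol*

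**What the plan says.** Section 4.2 of the protocol opens with a default time for all exclusions: "Subjects will be excluded from the study if they satisfy any of the following criteria at the screening visit unless otherwise stated". Exclusion 12 reads "Positive hepatitis panel, positive syphilis test, and/or positive human immunodeficiency virus test" and refers to Appendix 2 for the tests. It names no visit. Exclusion 11, immediately above it, does: "Positive alcohol breath test result or positive urine drug screen (confirmed by repeat) at screening or check-in".

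The amended schedule in Appendix 6 has one row for viral serology, "Serology for HIV-1/HIV-2 antibodies and p24 antigen, HBsAb, HBcAb, HBsAg, or HCVAb". Its only mark is in the Day -2 column, and the Screening column (Days -28 to -3) is blank. No row names syphilis.

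Section 7 fixes the periods: "This study includes a screening period (Day -28 to Day -3), a treatment period (Days -2 to 19", so Day -2 lies outside screening. Section 3.1 is looser: "screening procedures and tests to establish subject eligibility to enter the study will be performed within 28 days before Day 1".

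Appendix 2 lists syphilis, the HIV tests and four hepatitis markers under serology: "Anti-hepatitis B surface antibody Anti-hepatitis B core antibody Hepatitis B surface antigen Hepatitis C antibody". It does not say which of these results makes the hepatitis panel positive.

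**The concern.** A criterion that must be judged at screening has no screening test behind it, and one of its three parts has no scheduled test by name. The site cannot follow both the criterion and the schedule, and must decide for itself which governs.

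The stake is subject protection and wasted admissions. Sections 1.1 and 1.2 describe CBP-307 as a drug that reduces circulating lymphocytes, and exclusion 12 is the safeguard against enrolling someone with one of the listed infections. If blood is first taken on the afternoon of admission, the result may still be outstanding when the Day -1 placebo dose and baseline recording begin, and possibly when the first CBP-307 dose is due. If the result is positive and arrives in time, the failure is still found only after the subject has occupied a bed and perhaps completed a baseline Holter day.

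**Working it through.** No formula or stated figure is at issue. The check compares the provisions and counts days.

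**When exclusion 12 is judged.** The Section 4.2 default is the screening visit unless a criterion says otherwise. Exclusion 12 does not say otherwise, while exclusion 11 names check-in. The authors therefore named check-in where they meant it, and the default governs exclusion 12.

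**When the test is drawn.** Both printings of the amended Appendix 6, and the current-text table in the Summary of Amended Protocol Changes, put the single serology mark on Day -2. In the same tables the single mark for admission falls on Day -2 and the single mark for follicle-stimulating hormone falls on Screening. The first two columns are therefore kept apart correctly, and a slip in reading the table is unlikely.

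**Which period Day -2 belongs to.** Section 7 ends screening on Day -3 and starts the treatment period on Day -2. A Day -2 draw is not a screening-visit draw.

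**Syphilis.** It is required by exclusion 12, listed in Appendix 2 and counted in the blood volume of Appendix 3, but no schedule row names it. Its timing is unstated.

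**Time available.** The schedule has no Day 0. Footnote 1 to Appendix 6 has subjects arriving in the afternoon of Day -2. Dosing is in the morning, and the Day -1 recording follows the same clock times.

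| Draw | To Day -1 procedures | To Day 1 dose |
|---|---|---|
| Day -2, afternoon | less than 1 day | about 1.5 days |
| Screening, Day -3 | 2 days | 3 days |
| Screening, Day -28 | 27 days | 28 days |

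The documents give no laboratory turnaround time, so whether 1.5 days is enough cannot be settled from them.

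**Is there a hold?** Section 4.3 assigns numbers to eligible subjects before the first dosing occasion, and Section 5.3 with Appendix 6 puts randomization on Day 1. These make dosing conditional on eligibility in general. Neither says that the serology and syphilis results must be in hand, and neither addresses the Day -1 procedures by name.

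**The case against.** The strongest reply is that the criterion still works in practice. Appendix 6 schedules an eligibility review on Day -2 as well as at screening. Section 3.1 allows eligibility tests at any time within 28 days before Day 1, which covers Day -2. Inclusion 3 has good health, including laboratory evaluations, confirmed at check-in. Only eligible subjects are numbered before dosing, and randomization is on Day 1. All of this stands. A reader might infer that exclusion 12 cannot be applied at all, or that infected subjects will be dosed. The documents support neither: a prompt Day -2 result can exclude a subject before randomization, and late dosing would need a slow laboratory together with a site that proceeds while eligibility is open.

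A second reply is that table columns in the extracted text are not always reliable. Some marks in late columns do shift by one between copies. That is a fair caution, but the three copies of the amended schedule agree on this row, and its neighbours in the first two columns are placed sensibly. The finding does not rest on any difference from the superseded schedule, which would not be an error in itself.

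A reader might also infer that the hepatitis panel treats an isolated hepatitis B surface antibody as a positive result, and so removes volunteers who are merely immune. The protocol does not say this. Exclusion 12 leaves the term undefined, Appendix 2 only lists the marker, and vaccination-derived antibody is never mentioned. Any estimate of extra screening failures would need a prevalence that the documents do not give.

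**Conclusion.** The point holds as a mismatch between a criterion and the schedule. Exclusion 12 is a screening-visit criterion, its viral tests are marked only on Day -2, its syphilis test is in no named row, and nothing explicitly requires the results before the Day -1 baseline procedures or the Day 1 dose. In size, the interval to the first CBP-307 dose is about 1.5 days instead of 3 to 28. There is no effect on power, alpha or the QTc conclusion.

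This rests on two readings: that the serology mark is truly in the Day -2 column, and that Section 7 governs which days count as screening. What makes the hepatitis panel positive is a separate ambiguity for the sponsor to clarify. No clinical rule is proposed here.

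**What to change.** Reconcile Appendix 6 with exclusion 12 in one of two ways: mark serology in the Screening column and add syphilis to that row, using blood already drawn at that visit; or add check-in to exclusion 12, as exclusion 11 does, and add syphilis to the Day -2 row. In either case, state that all exclusion 12 results must be available before Day -1 procedures begin. Keep the HIV and syphilis parts of exclusion 12. Ask the sponsor to state which Appendix 2 markers make the hepatitis panel positive.

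The cost is one schedule row and one or two sentences. No extra visit is needed, and no extra blood: hematology and chemistry are already drawn at screening, and Appendix 3 already counts serology and syphilis within its five laboratory draws (5 × 12.5 mL = 62.5 mL).

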3. **Screening and Check-in on Day -2:** Tympanic temperature, respiratory rate, and supine pulse rate and blood pressure. **Other days (except for Days 17, 18, and 19):** Prior to and 2 hours after dosing, supine vital signs (tympanic temperature, pulse rate, respiratory rate, and blood pressure). **Days 17 and 18:** Tympanic temperature, respiratory rate, and supine pulse rate and blood pressure at approximately the same time each day. **Discharge (Day 19):** Prior to discharge, supine vital signs (tympanic temperature, pulse rate, respiratory rate, and blood pressure). **End of Study/Follow-up Visit (Day 29±2 days):** Tympanic temperature, respiratory rate, and supine pulse rate and blood pressure.

4. 12-lead safety ECG will be recorded in triplicates before dosing and in singles 2 hours postdose on all study days (except for Days 17 and 18) and before discharge on Day 19. Postdose safety will be interpreted on-site by the investigator and may be repeated to confirm/refute clinically abnormal findings.
5. Continuous cardiodynamic monitoring (Holter) will be performed for 25 hours on Day -1 (baseline), 1, 6, 15, and 16. The recording will be started at least 1 hour before dosing and at the corresponding clock time on Day -1. Replicate 12-lead ECGs will be extracted from the continuous recording prior to dosing (-30 minutes) and 0.5, 1, 2, 3, 4, 6, 8, 12, and 24 hours postdose on each day. At timepoints for ECG extractions, subjects will be supinely resting in an undisturbed environment. The ECG effects of CBP-307 will be tested on data from Day -1 (baseline for both groups), Day 6 (therapeutic concentrations versus placebo), and Day 15 (supratherapeutic concentrations versus placebo). Assay sensitivity with moxifloxacin will be tested on data from Days -1, 1, 15, and 16.
6. Serum pregnancy test will be performed at screening and urine pregnancy tests will be performed on Day -2 and at the follow-up visit (Day 29±2 days). A positive urine pregnancy test will be confirmed with a serum pregnancy test.
7. Pharmacokinetic samplings will be performed prior to dosing and 0.5, 1, 2, 3, 4, 6, 8, 12, and 24 hours after dosing on each PK sampling day (Days 1, 6, 15, and 16). Additional PK samples will be collected at 72 and 96 hours following dosing on Day 15.

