8. Allowable assessment/sample collection windows are as follows: ±2 minutes for 0.5 hours postdose, ±5 minutes for 1 hour postdose, ±15 minutes for ECGs and vital sign measurements at 2 hours postdose and ±5 minutes for PK sampling at 2 hours postdose, ±5 minutes for 3 to 4 hours postdose, ±10 minutes for 6 to 8 hours postdose, and ±30 minutes for 12 to 24, 72, and 96 hours postdose.
9. Subjects will be monitored via cardiac telemetry during the treatment period from approximately 1 hour prior to dose administration and until approximately 12 hours postdose on Days 1, 2, 3, and 7 (up-titration days). Based on the emerging safety data from the study, the duration of the telemetry may be extended if necessary. The start and stop date and time of the telemetry monitoring will be recorded in the eCRF.

Summary of Amended Protocol Changes

A Phase I, Single-center, Randomized, Double-blind, Double-dummy, Placebo- and Positive-Controlled Study to Investigate the Effects of CBP-307 on the QTc Interval in Healthy Subjects

Protocol Amendment 1 Status: Final
Original Protocol Date: 18 March 2021
Protocol Amendment 1 Date: 10 May 2021

Investigational Medicinal Product: CBP-307

Protocol Reference Number: CBP-307AU002
Covance Study Number: 8463245
IND Number: 134585

Sponsor:
Connect Biopharma Australia Pty Ltd.
[name]
Australia

Suzhou Connect Biopharmaceuticals, Ltd.
[name]
[name]
[name]
[name]
China

Sponsor Signatory:
[name]

Study Site:
CMAX
[name]
Australia

Principal Investigator:
[name]

Information described herein is confidential and may be disclosed only with the express written permission of the Sponsor.

The primary changes in this amendment, along with the rationale for the/each change as appropriate, are:

1. Update the protocol to add a new CBP-307 dose group (0.05 mg) in the up-titration period.
2. Update the applicable assessment timepoints throughout the protocol to align with the additional dose group added in the up-titration period.
3. Update the protocol to include additional pharmacokinetic (PK) sample collections at 72 and 96 hours after the final CBP-307 dose on Day 15 to better capture the terminal phase PK parameters of CBP-307 after 0.5 mg multiple doses.
4. Update the protocol to include additional PK parameters.

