For the repeated-dose administration of CBP-307, the C_{max} and AUCs increased with the higher administered dose (Table 2). At the steady-state timepoint on Day 28, the median CBP-307 t_{max} was 4 to 6 hours. The average $t_{1/2}$ was similar, ranging 44 to 49 hours, and there were no dose-dependent changes in $t_{1/2}$ within the dose range. The $t_{1/2}$ was slightly prolonged after repeated-dose administration when compared with that after a single-dose administration. Moderate accumulation of CBP-307 (approximately 3 times the levels

following a single dose) was noted in plasma after QD administration for 14 consecutive days.

Table 2: Pharmacokinetics Parameters in the Multiple-Dose CBP-307 Regimen (Study CBP-307AU001)

Multiple-Dose Regimen PK Parameters	Multiple-Dose Cohort 1 CBP-307 Dosing, mg (\pm SD) (n)		Multiple-Dose Cohort 2 CBP-307 Dosing, mg (\pm SD) (n)	
	Day 1 0.1	Day 28 0.25	Day 1 0.15	Day 28 0.15
AUC ₀₋₂₄ (ng*h/mL)	24.5 \pm 3.26 (n = 5)	125 \pm 12.4 (n = 4)	26.3 \pm 7.45 (n = 5)	79.7 \pm 27.3 (n = 6)
AUC _{last} (ng*h/mL)	NA	203 \pm 21.9 (n = 4)	NA	131 \pm 44.7 (n = 6)
C _{max} (ng/mL)	1.45 \pm 0.214 (n = 5)	6.30 \pm 0.588 (n = 4)	1.32 \pm 0.422 (n = 6)	4.23 \pm 1.45 (n = 6)
t _{max} (hours)	6.80 \pm 1.50 (n = 5)	6.50 \pm 1.50 (n = 4)	5.00 \pm 0.68 (n = 6)	4.33 \pm 0.33 (n = 6)

Abbreviations: AUC₀₋₂₄ = area under the curve from time 0 to 24 hours; AUC_{last} = area under the curve at the last time point; C_{max} = maximum concentration; mg = milligram(s); NA = not applicable; ng/mL = nanogram(s) per milliliter; PK = pharmacokinetic; SD = standard deviation; T_{max} = time to maximum concentration.

Source: Final report for Study CBP-307AU001.

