Approximately 64 healthy subjects (at least 30% for each sex) will be randomized into 2 groups (Group 1 and 2) with 32 subjects in each. Group 2 consists of 2 sub-groups (Group 2A and 2B) and each sub-group will be randomized with 16 subjects. Subjects will be randomized to receive a treatment sequence that includes 4 treatments (CBP-307 therapeutic dose, CBP-307 supratherapeutic dose, moxifloxacin, or placebo [matched to CBP-307 or moxifloxacin]); assigned study treatments will be administered on Day 1, Day 2, Days 3 to 6, Days 7 to 15, and Day 16. Dosing details are provided in [Table 3](#). Blood samples for pharmacokinetic analysis will be collected predose and at each postdose cardiodynamic electrocardiogram timepoint. Additional PK samples will be collected at 72 and 96 hours following dosing on Day 15. An end-of-study visit will occur on Day 29±2 days.

Potential subjects will be screened to assess their eligibility to enter the study within 27 days prior to the first dose administration. Subjects will be admitted into the study site on Day -2 and will remain at the study site until discharge on Day 19. Treatment administration will occur on Days 1, 2, 3 to 6, 7 to 15, and 16 under fasting conditions (all subjects will receive placebo on Day -1). Continuous cardiodynamic ECG monitoring and recording will begin at least 25 hours prior to the administration of study treatments on Day 1 and continue through 24 hours after the administration of study treatments on Days 1, 6, 15, and 16 and at corresponding timepoints on the day before dosing, ie, Day -1. Blood samples for PK analysis will be collected predose and at each postdose cardiodynamic ECG timepoint. Additional PK samples will be collected at 72 and 96 hours following dosing on Day 15. Subjects will return to the study site for a follow-up visit on Day 29±2 days.

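### One copy of the Appendix 6 schedule marks CBP-307/placebo dosing on Day 16, while the design text, Table 3 and that schedule's own footnotes point to Day 15 as the last CBP-307 day

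*Protocol*

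**What the plan says.** The file holds more than one version of the protocol. The first Appendix 6 schedule belongs to text that names Labcorp for SAE reporting and has revised sampling windows in footnote 8. It therefore appears to be later than Amendment 1, which names Covance.

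- **First Appendix 6 schedule.** The row "CBP-307/placebo administration" is marked on Days -1, 1, 2, 3 to 5, 6, 7 to 14, 15 and 16. The row "Moxifloxacin/placebo administration" is marked on Days 1 and 16.
- **Footnotes to that schedule.** Footnote 7: "Additional PK samples will be collected at 72 and 96 hours following dosing on Day 15". Footnote 2: "Discharge from unit will occur after the 96-hour PK samples and after completion of safety assessments on Day 19".
- **Amendment 1, Section 3.1.** The dose list reads "A supratherapeutic dose of CBP-307 (0.5 mg, Days 7 to 15" and has no CBP-307 dose after that.
- **Amendment 1, Section 5.1, Table 3.** On Day 16 each group has one tablet, moxifloxacin or its placebo. No group has a capsule.
- **Amendment 1, Appendix 6.** The same row is marked up to Day 15 and blank on Day 16.
- **Amendment 1, summary of changes.** The late samples were added at "72 and 96 hours after the final CBP-307 dose on Day 15", to capture the terminal phase.

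**The concern.** A row that governs drug administration should agree with the dosing table and with the sampling plan that hangs on it. Here one copy of the row runs a day longer than the other passages.

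Two things would be at stake if the mark were acted on as active drug. The first is exposure: Group 1 (32 planned healthy subjects) would receive one more dose at the highest level than the design states. The second is the terminal-phase pharmacokinetics. The 72 and 96 h samples are there to follow decline after the last dose, and they do so only if nothing is given after Day 15. Section 8.4 lists the elimination rate constant, half-life and AUC to infinity, all of which use that decline.

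**Working it through.** **1. Mark count.** The part of the table that holds this row has 14 day columns.

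| Schedule | Marks in the CBP-307/placebo row | Last marked day |
|---|---|---|
| First Appendix 6 schedule | 8 | 16 |
| Amendment 1, Appendix 6 | 7 | 15 |
| Amendment 1, summary of changes (new text) | 7 | 15 |

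Neighbouring rows of the first schedule line up with the footnotes: Holter on Days -1, 1, 6, 15 and 16 (footnote 5), and PK on Days 1, 6, 15, 16, 18 and 19 (footnote 7).

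**2. The plan's own figures.** Days 7 to 15 give 15 − 7 + 1 = 9 doses of 0.5 mg. Counting from Day 15, 72 h is Day 18 and 96 h is Day 19. This matches the PK marks and the discharge day, so the sampling plan is consistent with a last dose on Day 15.

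**3. If Day 16 were active drug in Group 1.** Doses of 0.5 mg: 16 − 7 + 1 = 10. Time from last dose to the late samples: 72 − 24 = 48 h and 96 − 24 = 72 h.

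**4. Effect on the late concentrations.** Inputs:
- Doses from Section 3.1: 0.05 mg on Day 1, 0.1 mg on Day 2, 0.2 mg on Days 3 to 6, 0.5 mg on Days 7 to 15.
- Repeated-dose half-life from Section 1.2.1.2, "ranging 44 to 49 hours".
- Assumed: linear one-compartment kinetics, with absorption complete by the sampling times. Absorption rates of 0.3 to 1.0 per h left the ratios unchanged.

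Let r = 2^(−24/half-life) be the fraction left after one day, and let L be the sum over Days 1 to 15 of dose × r^(15 − day). The planned level at 72 h is proportional to L·r³. A Day 16 dose adds 0.5·r². The ratio at 72 h, and equally at 96 h, is 1 + 0.5/(L·r).

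- 44 h: r = 0.685, L = 1.553, ratio = 1 + 0.5/1.064 = 1.47.
- 49 h: r = 0.712, L = 1.681, ratio = 1 + 0.5/1.197 = 1.42.

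**5. Effect on a fitted half-life.** Take a log-linear fit through 24, 72 and 96 h. The 24 h sample precedes any Day 16 dose, so only the later two points move. The mean time is 64 h, the deviations are −40, 8 and 32, and the sum of squares is 1600 + 64 + 1024 = 2688. The slope shifts by ln(ratio) × (8 + 32)/2688.

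- 44 h: −0.01575 + 0.385 × 0.01488 = −0.01002 per h, so half-life = 0.6931/0.01002 = 69.2 h.
- 49 h: −0.01415 + 0.349 × 0.01488 = −0.00895 per h, so half-life = 77.4 h.

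Both are about 57% to 58% too long (69.2/44 = 1.57; 77.4/49 = 1.58). A slope through 72 and 96 h alone is unchanged, because both points rise by the same factor.

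**The case against.** Four objections carry weight.

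*The mark may not be on the printed page.* Other schedule rows in the text read from the PDF are displaced. Hematology, chemistry and urinalysis fall on Days 18 and 19 in the summary of changes but on Days 19 and 29 in Amendment 1's Appendix 6, although both show the same schedule. In the summary of changes the safety ECG falls on Day 18, which footnote 4 excludes. A stray mark cannot be ruled out. This row does fill its 14 columns and its neighbours align, so the mark is more than noise, but it needs checking at source.

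*The comparison crosses versions.* Section 3.1 and Table 3 as quoted come from Amendment 1. The counterparts in the version that holds the marked schedule are not shown. It cannot be said that its Table 3 contradicts it. Within that version, the evidence is footnotes 2 and 7.

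*The row does not order active drug.* It covers CBP-307 or placebo and gives no dose. It also marks Day -1, when "all subjects will receive placebo on Day -1". A reader might infer that a site following the schedule would give a tenth 0.5 mg dose. The documents do not support that: Section 3.1 refers to Table 3 for dosing details, and Amendment 1's Table 3 has no capsule on Day 16. For the same reason, reading the mark as placebo does not remove the mismatch with that table.

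*The main analyses are untouched.* This stands. Section 8.3 models CBP-307 on Days 1, 6 and 15, and assay sensitivity uses Groups 2A and 2B, which receive no active CBP-307.

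**Conclusion.** As the text reads, the Day 16 mark conflicts with Amendment 1's design text, Table 3 and schedule, and it sits badly with footnotes 2 and 7 of the schedule in which it stands. The passages must be reconciled.

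The consequences are conditional. Only if the mark were carried out as active drug in Group 1 would there be ten 0.5 mg doses instead of nine, late concentrations about 42% to 47% higher, and a half-life of about 69 to 77 h from a fit through 24, 72 and 96 h. These sizes assume linear kinetics and apply to 0.5 mg the half-life of 44 to 49 h observed at 0.15 and 0.25 mg daily. A reader might conclude that the terminal half-life would be lost however it is fitted; a slope through 72 and 96 h alone would not change under this model.

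The reach is limited to subject exposure and terminal-phase pharmacokinetics. It still merits correction before use, because the row concerns dosing of healthy subjects and the repair is trivial.

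**What to change.** Check the Day 16 cell of the CBP-307/placebo row against the source page. If the mark is there, reconcile the row with Section 3.1, Table 3 and footnotes 2 and 7 of the same protocol version, so that one last CBP-307 dosing day holds throughout. State in the row or a footnote whether any Day 16 capsule is active or placebo. If active dosing on Day 16 is intended, the anchor of the 72 and 96 h samples, the discharge footnote and the terminal-phase parameters need matching edits. Which passage is right is for the sponsor to decide.

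The cost is one cell, or a few matching edits in the table and footnotes. Aligning the text adds no procedures or subjects.
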